**LY3074828**

Study I6T-MC-AMAF is a Phase 2, multicenter, randomized, placebo-controlled study of LY3074828 in subjects with moderate-to-severe plaque psoriasis. The study consists of a double-blind, 16-week induction period where subjects will receive 1 of 4 treatment arms (LY3074828 30 mg, 100 mg, 300 mg, or placebo) at baseline and Week 8, a maintenance period consisting of 88 weeks of treatment, and 16 weeks of follow-up.

Eli Lilly and Company  
Indianapolis, Indiana USA 46285

Protocol Electronically Signed and Approved by Lilly on 24-May-2016.  
Amendment (a) Electronically Signed and Approved by Lilly: 20 December 2017  
Amendment (b) Electronically Signed and Approved by Lilly  
on approval date provided below.

Approval Date: 21-Aug-2018 GMT

## 1. Synopsis

### Title of Study:

A Phase 2, Multicenter, Randomized, Parallel-Arm, Placebo-Controlled Study of LY3074828 in Subjects with Moderate-to-Severe Plaque Psoriasis.

### Rationale:

Study I6T-MC-AMAF (AMAF) is a Phase 2 study designed to determine whether subcutaneous (SC) administration of LY3074828, CCI [REDACTED] monoclonal antibody that is directed against the p19 subunit of IL-23, is safe and efficacious in subjects with moderate-to-severe plaque psoriasis. This study will help determine the clinical activity defined by improvement in skin disease severity measures and key patient reported outcomes measures, as well as safety findings, that will support design of Phase 3 studies.

### Objective(s)/Endpoints:

Objectives	Endpoints

Primary
 
To test the hypothesis that treatment with LY3074828 is superior to placebo in inducing PASI 90 response at Week 16 in subjects with moderate-to-severe plaque psoriasis
	
The proportion of subjects achieving PASI 90 at Week 16 (NRI)

Secondary
 
 
To evaluate the safety and tolerability of treatment with LY3074828
 
To evaluate the efficacy of treatment with LY3074828 compared to placebo in inducing PASI 100 and PASI 75 at Week 16
 
To evaluate the efficacy of treatment with LY3074828 compared to placebo in inducing sPGA 0 (clear) and sPGA 0/1 at Week 16
 
To evaluate the effect of LY3074828 on patient reported outcome measures: PSS, PatGA, DLQI, and SF-36 at Week 16
 
To characterize the long-term efficacy of LY3074828 on the PASI 100, PASI 90, and PASI 75 responses at Week 52, 104, and 120
 
To characterize the long-term efficacy of LY3074828 on patient reported outcome measures PSS, PatGA, DLQI, and SF-36 at Weeks 52, 104, and 120
 
To characterize the PK of LY3074828
 
	
 
Adverse event and discontinuation rates
 
The proportion of subjects achieving PASI 100 and PASI 75 at Week 16 (NRI)
 
The proportion of subjects achieving sPGA 0 and sPGA 0/1 at Week 16 (NRI)
 
The mean change from baseline for PSS, PatGA, DLQI, and SF-36 at Week 16
 
The proportion of subjects achieving PASI 100, PASI 90, and PASI 75 at Weeks 52, 104, and 120
 
The mean change from baseline for PSS, PatGA, DLQI, and SF-36 at Weeks 52, 104, and 120
 
Clearance and volume of distribution
 

Abbreviations: DLQI = Dermatology Life Quality Index; NRI = nonresponder imputation; PASI = Psoriasis Area and Severity Index; PASI 75 = 75% improvement in PASI from baseline; PASI 90 = 90% improvement in PASI from baseline; PASI 100 = 100% improvement in PASI from baseline; PatGA = Patient Global Assessment; PK = pharmacokinetics; PSS = Psoriasis Symptom Scale; SF-36 = Short-Form Health Survey; sPGA = static Physician's Global Assessment.

**Summary of Study Design:**

Study AMAF is a multicenter, randomized, parallel-arm, placebo-controlled trial with 4 study periods in subjects with moderate-to-severe plaque psoriasis. Subjects who complete the third study period may be eligible to participate in a separate long-term extension study as an alternative to participating in the fourth AMAF study period.

**Treatment Arms and Duration:**

The study will include 4 arms: 3 experimental arms in which LY3074828 will be dosed SC at 30 mg, 100 mg, or 300 mg and 1 placebo comparator arm. During the double-blind, 16-week induction period, study drug will be administered at Week 0 and Week 8. At the end of the induction period (Week 16), subjects will continue treatment in the maintenance period which is intended to explore 1 of 2 treatment strategies through Week 104. Dose levels in the maintenance period will remain double-blind; however, dosing strategy will be open-label. The maintenance period consists of 88 weeks of treatment. All placebo subjects and subjects assigned to treatment with LY3074828 who have a <90% improvement in Psoriasis Area and Severity Index (PASI) from baseline (PASI 90) at Week 16 will receive LY3074828 300 mg SC every 8 weeks (Q8W) during the entire maintenance treatment period. Subjects with  $\geq$ PASI 90 (as needed [PRN] dosing group) at Week 16 will only be dosed with LY3074828 at the baseline dose level assignment no more frequently than Q8W when disease activity level is <PASI 90, and this will continue until  $\geq$ PASI 90 is regained. The maintenance period will be followed by a 16-week follow-up period to assess subject safety and study drug efficacy. Subjects who complete the maintenance period may be eligible to participate in separate long-term extension study.

**Number of Subjects:**

Approximately 200 subjects will be randomized at a 1:1:1:1 ratio in the blinded induction dosing period to LY3074828 30 mg, 100 mg, 300 mg, and placebo (50 subjects per dosing regimen, respectively). Randomization will be stratified by prior exposure to biologic therapy for psoriasis use (yes/no).

**Statistical Analysis:**

Induction period analyses of efficacy and health outcomes will be conducted on the intent-to-treat (ITT) population. Maintenance period analyses of efficacy and health outcomes will be conducted on ITT subjects who receive at least 1 dose of study treatment and who enter the maintenance period at Week 16 (Visit 7). Safety analyses will be conducted on the safety population.

The primary analysis method for treatment comparisons of categorical efficacy and health outcome variables will be a logistic regression analysis with treatment, geographic region, and previous exposure to biologic therapy (yes/no) in the model, using the nonresponder imputation (NRI) method.

The primary analysis method for treatment comparisons of the continuous efficacy and health outcome variables will be a mixed-effects model for repeated measures (MMRM) analysis with treatment, geographic region, previous exposure to biologic therapy (yes/no), baseline value, visit, treatment-by-visit interaction, and baseline-by-visit interaction in the model as fixed factors.

No multiplicity control procedures will be used in the testing of the primary endpoint in this study. Fisher's exact test will be used for all adverse events (AE), baseline, discontinuation, and other categorical safety data. Continuous vital sign and laboratory values will be analyzed by an analysis of covariance (ANCOVA) with treatment and baseline value in the model.

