#### **10.3.1.1. General Considerations for Analyses in the Induction Period**

Continuous data will be summarized in terms of the mean, standard deviation, minimum, maximum, median, and number of observations. Categorical data will be summarized as frequency counts and percentages. Comparisons between each LY3074828 dose regimen (30 mg, 100 mg, 300 mg) and placebo will be performed for all analyses in the induction period with no adjustment for multiple comparisons.

For the induction period efficacy, health outcomes, and safety analyses, baseline is defined as the last available value before the initial randomization, which in most cases will be the measure recorded at Week 0 (Visit 2). Change from baseline will be calculated as the visit value of interest minus the baseline value.

Treatment comparisons of categorical efficacy variables will be conducted using a logistic regression analysis with treatment, geographic region (US/Non-US), and prior exposure to biologic therapy use (yes/no) in the model. The proportions and 95% confidence intervals will be reported.

Treatment comparisons of continuous efficacy and health outcome variables will be made using mixed-effects for repeated measures (MMRM).

When MMRM is used, the model includes treatment, geographic region (US/Non-US), prior exposure to biologic therapy use (yes/no), baseline value, visit, and the interaction of treatment-by-visit as fixed factors. The covariance structure to model the within-subject errors will be unstructured. If the unstructured covariance matrix results in a lack of convergence, the heterogeneous Toeplitz covariance structure, followed by the heterogeneous autoregressive covariance structure will be used. The Kenward-Roger method will be used to estimate the denominator degrees of freedom. Type III sums of squares for the least squares means will be used for the statistical comparison; the 95% confidence interval will also be reported. Treatment group comparisons with placebo at Week 16 (Visit 7) and all other visits will be tested.

Fisher's exact test will be used for categorical safety data including AE, baseline, and discontinuations. Continuous vital sign and laboratory values will be analyzed by analysis of covariance (ANCOVA) with treatment and baseline value in the model. Other continuous safety variables will be analyzed by t-tests, unless otherwise stated.

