5.2. Determination of Sample Size

Approximately 200 subjects will be randomized at a 1:1:1:1 ratio in the blinded induction dosing period to LY3074828 30 mg, 100 mg, 300 mg, and placebo (50 subjects per dosing regimen, respectively). Randomization will be stratified by prior exposure to biologic therapy for psoriasis (yes/no).

Assuming 60% and 3% PASI 90 response rates at 16 weeks for LY3074828 and placebo, respectively, pairwise comparisons to placebo have over 99% power using a 2-sided Fisher's exact test at the 0.05 significance level, with no adjustment for multiple comparisons.

As results for PRN dose arms in the Maintenance Period will support the maintenance dosing strategy in Phase 3 planning, a reasonable total number of subjects who completed 1-3 visits in the Maintenance Period (Week 20 to Week 28) will be needed. Based on study simulations under the treatment effect scenario outlined above, approximately 49 subjects (9 on 30 mg, 18 on 100 mg, 22 on 300 mg PRN arms) will have completed the Week 20 visit at the time of the primary endpoint datalock.

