The analysis method for comparisons of each Induction Period LY3074828 dose regimen (300 mg, 100 mg, 30 mg) and placebo for the continuous efficacy and health outcome variables will be a Mixed effect Model Repeat Measurement (MMRM) analysis when the endpoint is collected at multiple postbaseline visits during a study period, or analysis of covariance (ANCOVA) when the endpoint is collected at one postbaseline visit during a study period, or for sensitivity analyses. When the MMRM model is used, the model will include treatment, geographic region (US/OUS), previous therapy (yes/no), baseline value, visit, and the interaction of treatment-by-visit as fixed factors. When the ANCOVA model is used, the model will include baseline value as a continuous covariate and treatment, geographic region (US/OUS), and previous therapy (yes/no) as fixed factors. For both models, the covariance structure to model the within-patient errors will be unstructured. The Restricted Maximum Likelihood (REML) will be used. The Kenward-Roger method will be used to estimate the denominator degrees of freedom. If the unstructured covariance matrix results in a lack of convergence, the heterogeneous Toeplitz covariance structure, followed by the heterogeneous autoregressive covariance structure, followed by the compound symmetry will be used. This order is specified according to a decreasing number of covariance parameters in the structure. Type III tests for the least squares (LS) means will be used for the statistical comparison; the 95% CI will be reported. Dosing regimen comparisons at Week 16 (Visit 7) and all other postbaseline visits in the Induction Period will be reported.

Proportions and 95% confidence intervals will be summarized for binary outcomes observed in the Maintenance Period. Mean change from baseline and 95% confidence intervals will be summarized for continuous outcomes observed in the Maintenance Period.

The Kaplan-Meier product limit method will be used to estimate the survival curves for post induction (includes Maintenance and Follow-up Periods) time-to-event variables (time to loss of response, time to response recapture after loss of response); median times will be summarized by treatment.

Time to First Loss of Response in the Maintenance Period for PRN Patients

Time to first loss of response (PASI 90 or PASI 100) in the Maintenance Period includes only those subjects who achieved the respective response at Week 16 and is defined in weeks as:

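### The synopsis MMRM includes a baseline-by-visit term that protocol 10.3.1.1 and the SAP omit; if baseline slopes vary by visit, omitting it can cost precision at Week 16

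*Protocol*

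**What the plan says.** The protocol synopsis (Statistical Analysis) makes an MMRM the main method for continuous efficacy and health outcome variables. Its fixed factors are treatment, region, prior biologic exposure, baseline and visit, followed by "treatment-by-visit interaction, and baseline-by-visit interaction in the model as fixed factors".

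Protocol 10.3.1.1 gives the same list without the last term, ending at "baseline value, visit, and the interaction of treatment-by-visit as fixed factors". SAP 6.1.3 and 6.2.2 do the same. No text explains the difference. It is still present in protocol amendment (b), approved on 21 August 2018, after SAP version 2 of 28 June 2017.

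On covariance, SAP 6.1.3 says "the covariance structure to model the within-patient errors will be unstructured", with simpler structures if the model does not converge. Endpoints measured once after baseline in a period are routed to "analysis of covariance (ANCOVA) when the endpoint is collected at one postbaseline visit during a study period". In induction that applies to SF-36, which is collected only at Visits 2 and 7. SAP Table 6.3 assigns MMRM in induction to PASI change, BSA, PSSI, DLQI, PatGA and PSS.

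**The concern.** The protocol disagrees with itself, and its synopsis disagrees with the SAP, about the model behind three listed secondary endpoints: Week 16 change in DLQI, PatGA and PSS. Two analysts working from different sections could report different Week 16 estimates, intervals and p-values, and each could claim to have followed the plan.

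The two models also differ in substance. Without baseline-by-visit, a single regression slope of change on baseline serves Weeks 2, 4, 8, 12 and 16. For a severity score that treatment drives toward zero, the change moves away from zero, roughly in proportion to baseline. Little response has accrued by Week 2, so the slope there is likely to be shallow. By Week 16 it is likely to be steeper. A common slope then falls short at Week 16. Part of the baseline variation stays in the Week 16 residual, and chance baseline differences between arms of about 50 are only partly removed.

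**Working it through.** **1. The plan's own figure.** The only readable power statement concerns the primary endpoint and does not use the MMRM. "Approximately 200 subjects will be randomized at a 1:1:1:1 ratio", so there are 50 per arm. "Assuming 60% and 3% PASI 90 response rates at 16 weeks", the SAP says that "pairwise comparisons to placebo have over 99% power" with a "2-sided Fisher's exact test at the 0.05 significance level, with no adjustment for multiple comparisons". Exact enumeration with 50 versus 50, 60% versus 3%, gives power 0.9999999. The figure reproduces, and the present point does not touch it.

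**2. Inputs for the MMRM comparison.** From the documents: 4 arms of 50, postbaseline visits at Weeks 2, 4, 8, 12 and 16, and an unstructured covariance. Assumed, because the documents give none: baseline SD, residual SDs, correlations, baseline slopes by visit, and 10% dropout in the simulations.

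**3. Large-sample formula.** With residual covariance S and visit slopes β, the common slope tends to b = 1′S⁻¹β / 1′S⁻¹1. The Week 16 standard error ratio (without / with baseline-by-visit) is

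ratio = √[1 + (β₁₆ − b)² × SD_base² / SD_res,16²].

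It equals 1 when the Week 16 slope equals the common slope. With baseline SD 8:

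- Early change, then flat (slopes −0.3, −0.6, −0.7, −0.7, −0.7), residual SD 5 and equal correlations: all visits get equal weight, so b = −3.0/5 = −0.60 and ratio = √(1 + 0.10² × 64/25) = √1.0256 = 1.013.
- Mild (−0.5 to −0.7), same covariance: b = −0.63 and ratio = √(1 + 0.07² × 2.56) = 1.006.
- Steep (−0.2 to −0.8), same covariance: b = −0.56 and ratio = √(1 + 0.24² × 2.56) = 1.071.
- Steep, residual SD rising from 3 to 6, autoregressive correlation 0.5: b = −0.36 and ratio = √(1 + 0.44² × 64/36) = 1.159.

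Over the whole grid (baseline SD 6 to 10) the ratio was 1.000 with equal slopes, 1.000 to 1.10 with mild variation and 1.002 to 1.75 with steep variation. The top value needs baseline SD 10, residual SD doubling over time and correlation 0.8 together.

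**4. Simulated MMRM fits.** Unstructured covariance, baseline SD 8, autoregressive correlation 0.7, 100 runs per row, both models fitted to the same data:

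| Slopes, Week 2 to Week 16 | Residual SD | SE without | SE with | Ratio |
|---|---|---|---|---|
| Equal | 5 throughout | 1.038 | 1.040 | 0.998 |
| Equal | rising 3 to 6 | 1.246 | 1.249 | 0.998 |
| Equal | falling 6 to 4 | 0.838 | 0.839 | 0.999 |
| Mild, −0.5 to −0.7 | 5 throughout | 1.052 | 1.042 | 1.010 |
| Mild | rising 3 to 6 | 1.280 | 1.253 | 1.022 |
| Mild | falling 6 to 4 | 0.843 | 0.838 | 1.005 |
| Steep, −0.2 to −0.8 | 5 throughout | 1.145 | 1.042 | 1.099 |
| Steep | rising 3 to 6 | 1.520 | 1.251 | 1.216 |
| Steep | falling 6 to 4 | 0.875 | 0.837 | 1.045 |
| Arm-specific percent reduction | 5 throughout | 1.231 | 1.166 | 1.055 |

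**5. Which row is nearest?** PASI 90 means a change of at least −0.9 × baseline, and the SAP assumes that 60% reach it on active drug. PASI simulated around that rate, 3% on placebo and the entry threshold of 12, with an assumed time course, gave pooled slopes moving from about −0.12 to −0.18 at Week 2 to −0.62 to −0.72 at Week 16 under gradual onset. Under fast onset they moved from about −0.3 to −0.7. The model standard error was 0.4% to 7% larger without the term. The empirical SD ratio was 0.97 to 1.05 over 150 runs per scenario, which shows no clear loss.

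**6. The same effect for a given imbalance.** With baseline SD 8 and 50 per arm, a one-SD chance difference in baseline means is 8 × √(2/50) = 1.6 points. The part left unadjusted at Week 16 is |β₁₆ − b| × 1.6. For the mild and steep equal-correlation cases in step 3, that is 0.07 × 1.6 = 0.11 and 0.24 × 1.6 = 0.38 points.

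**The case against.** The best defence is that the governing text is fairly clear. Protocol 10.3.3.2 sends the Week 16 health outcome comparisons to 10.3.1.1, not to the synopsis, and protocol 10.3.1 leaves full detail to the SAP. Body and SAP agree, so deleting the term from the synopsis would also end the contradiction. This stands: choosing the longer model is an efficiency argument and does not follow from the mismatch itself.

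A reader might infer that dropping the term necessarily widens the Week 16 standard error for every continuous endpoint, or costs this trial a definite share of its subjects. The documents do not support either. The loss is zero if the Week 16 slope equals the common slope, and no slope, SD or correlation is given from which a subject-equivalent could be worked out. SF-36 in induction goes to ANCOVA.

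The SAP also plans an mBOCF ANCOVA for PASI, BSA, PSSI and PSS. A single-visit ANCOVA estimates its own baseline slope and so avoids the constraint. That is only partial cover: it is a sensitivity analysis, it handles missing data differently, and it leaves out DLQI and PatGA.

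**Conclusion.** The mismatch is real and needs one answer. It concerns precision and clarity; nothing here shows bias in the randomised comparison. It does not reach the primary PASI 90 logistic regression or its power.

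Whether the omission costs anything depends on how far the baseline slope at Week 16 departs from the common slope. Visit-varying slopes are plausible, more so for PASI than for the patient-reported scales, but they are not established by the documents. Under the assumptions above, the Week 16 standard error is inflated by about 0% with equal slopes, 1 to 2% with mild variation and roughly 3 to 20% with steep variation. The upper end needs residual variance that grows over time as well as steep slopes. The simulations are small, and the five-visit set-up does not represent PSS if its weekly scores are the model visits. These figures are scenarios, not a forecast for this trial.

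**What to change.** Add baseline-by-visit to the MMRM in protocol 10.3.1.1 and in SAP 6.1.3 and 6.2.2, so that every section matches the synopsis.

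- **Cost with five postbaseline visits:** one term, 5 − 1 = 4 degrees of freedom, and no new data. If slopes are equal, the simulated ratio of 0.998 to 0.999 means essentially nothing is lost.
- **PSS:** SAP Appendix 2 derives weekly scores for Weeks 1 to 16. If these are the model visits, the term costs 16 − 1 = 15 degrees of freedom beside a 16 × 16 unstructured covariance. The SAP should state which visits enter the PSS model.
- **Maintenance:** SAP 6.2.2 is not confined to induction, and Table 6.3 also uses MMRM there for PASI, BSA and PSSI. The revised sentence should say whether the term applies in that period.

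If the Week 16 analysis has already been run, the clinical study report should name the model used and give the other as a sensitivity analysis.

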## 2. Schedule of Activities

Induction Dosing Period (Visits 1-7)								
Visit No.	V1	V2	V3	V4	V5	V6	V7	Comments
Week Relative to Study Drug Start	-4	0	2	4	8	12	16	All activities should be completed prior to any study dose administration unless otherwise stated below.
Day with Visit Tolerance Interval	≤28 from V2	0	14 ± 2	28 ± 3	56 ± 5	84 ± 5	112 ± 5	Visit 1 procedures may be conducted over more than 1 day as long as all tasks are completed within the allowable visit tolerance (at least 3 days should be allowed for receipt of laboratory test results).
Informed consent	X							
Demographics	X							
Height	X							
Physical examination & weight	X	X					X	One complete physical examination (excluding pelvic, rectal, and breast examinations) will be performed at screening. All physical examinations throughout the study should include a symptom-directed evaluation as well as examination of heart, lungs, and abdomen and visual examination of all skin areas (including genitalia and breast areas).
Review & confirm inclusion/exclusion criteria	X	X						
Complete medical/surgical history and habits	X							
Concomitant medications	X	X	X	X	X	X	X	
Preexisting conditions	X							
Adverse events	X	X	X	X	X	X	X	

Induction Dosing Period (Visits 1-7)								
Visit No.	V1	V2	V3	V4	V5	V6	V7	Comments
Week Relative to Study Drug Start	-4	0	2	4	8	12	16	All activities should be completed prior to any study dose administration unless otherwise stated below.
Day with Visit Tolerance Interval	≤28 from V2	0	14 ± 2	28 ± 3	56 ± 5	84 ± 5	112 ± 5	Visit 1 procedures may be conducted over more than 1 day as long as all tasks are completed within the allowable visit tolerance (at least 3 days should be allowed for receipt of laboratory test results).
Vital signs (BP and heart rate), body temperature only at V1 and V2, unless clinically indicated	X	X	X	X	X	X	X	Sitting blood pressure and pulse, to be obtained at approximately the same time as ECG measurements or blood sampling. When multiple assessments are scheduled for the same time point, the order of completion should be as follows: ECG, vital signs, and then blood sampling.
Chest radiography for TB screening (required only if not already done within 3 months prior to screening)	X							Chest radiography (Section 9.4.4.1) will be performed at screening unless such radiography has been performed within 3 months before initial screening (provided the radiographs and/or formal report are available for the investigator’s review).
PPD/QuantIFERON-TB Gold (per local guidelines)	X							Subjects will return 2 to 3 days after Visit 1 to have their PPD test read.
ECGs	X						X	This should be completed prior to any study dose administration or blood draw. Subjects should be supine for approximately 5 to 10 minutes before ECG collection and remain supine but awake during ECG collection.
C-SSRS	X	X	X	X	X	X	X	
CCI [REDACTED]		■	■	■	■	■	■	[REDACTED]
Study drug dosed		X			X		X	At Week 16, subjects will only receive study drug dosing if PASI <90.

Induction Dosing Period (Visits 1-7)								
Visit No.	V1	V2	V3	V4	V5	V6	V7	Comments
Week Relative to Study Drug Start	-4	0	2	4	8	12	16	All activities should be completed prior to any study dose administration unless otherwise stated below.
Day with Visit Tolerance Interval	≤28 from V2	0	14 ± 2	28 ± 3	56 ± 5	84 ± 5	112 ± 5	Visit 1 procedures may be conducted over more than 1 day as long as all tasks are completed within the allowable visit tolerance (at least 3 days should be allowed for receipt of laboratory test results).
Clinical Efficacy								
PASI	X	X	X	X	X	X	X	
sPGA	X	X	X	X	X	X	X	
PSSI, if applicable		X	X	X	X	X	X	Once a subject experiences symptoms related to scalp involvement, this form should be completed at all remaining indicated visits.
Whole body photographs		X					X	If subject has agreed to whole body photographs.
Health Outcomes								
PSS	Electronic Diary Taken Daily from Screening (V1) up to Week 16 (V7)						X	
PatGA		X	X	X	X	X	X	
DLQI		X	X	X	X	X	X	
SF-36		X					X	
Laboratory Tests								
Hematology	X	X	X	X	X	X	X	Unscheduled blood chemistry and hematology panels may be performed at the discretion of the investigator.
Lymphocyte subsets		X					X	
Serum chemistry	X	X	X	X	X	X	X	Unscheduled blood chemistry and hematology panels may be performed at the discretion of the investigator.
Urinalysis	X	X			X		X	

Induction Dosing Period (Visits 1-7)								
Visit No.	V1	V2	V3	V4	V5	V6	V7	Comments
Week Relative to Study Drug Start	-4	0	2	4	8	12	16	All activities should be completed prior to any study dose administration unless otherwise stated below.
Day with Visit Tolerance Interval	≤28 from V2	0	14 ± 2	28 ± 3	56 ± 5	84 ± 5	112 ± 5	Visit 1 procedures may be conducted over more than 1 day as long as all tasks are completed within the allowable visit tolerance (at least 3 days should be allowed for receipt of laboratory test results).
HBsAg, HBcAb, HBsAb	X							
HBV PCR	X					X		Any enrolled subject who is HBcAb+ will undergo monitoring of HBV PCR. Any subject with a positive HBV PCR test at any time must be discontinued from the study and receive appropriate follow-up medical care, including consideration for antiviral therapy.
Hep C antibody	X							Positive HCV antibody will be confirmed via HCV PCR.
HIV	X							
Immunogenicity		X	X	X	X	X	X	
Serum for LY3074828 concentrations (PK)		X	X	X	X	X	X	
Serum pregnancy test	X							To be performed only on women of child bearing potential.
Urine pregnancy test		X		X	X	X	X	To be performed only on women of child bearing potential.
FSH	X							FSH test is to be performed at screening for women who have had spontaneous amenorrhea for 6 to 12 months to confirm lack of childbearing potential.
hsCRP		X	X	X	X	X	X	
CCI		█					█	
		█			█		█	

Induction Dosing Period (Visits 1-7)								
Visit No.	V1	V2	V3	V4	V5	V6	V7	Comments
Week Relative to Study Drug Start	-4	0	2	4	8	12	16	All activities should be completed prior to any study dose administration unless otherwise stated below.
Day with Visit Tolerance Interval	≤28 from V2	0	14 ± 2	28 ± 3	56 ± 5	84 ± 5	112 ± 5	Visit 1 procedures may be conducted over more than 1 day as long as all tasks are completed within the allowable visit tolerance (at least 3 days should be allowed for receipt of laboratory test results).
CCI								

Maintenance Dosing Period (Visits 8-18)												
Visit No.	V8	V9	V10	V11	V12	V13	V14	V15	V16	V17	V18	Comments
Week Relative to Study Drug Start	20	24	28	32	36	40	44	48	52	56	60	All activities should be completed prior to any study dose administration unless otherwise stated below.
Day with Visit Tolerance Interval	140 ± 5	168 ± 5	196 ± 5	224 ± 5	252 ± 5	280 ± 5	308 ± 5	336 ± 5	364 ± 5	392 ± 5	420 ± 5	
Physical examination & weight				X					X			All physical examinations throughout the study should include a symptom-directed evaluation as well as examination of heart, lungs, and abdomen and visual examination of all skin areas (including genitalia and breast areas).
Concomitant medications	X	X	X	X	X	X	X	X	X	X	X	
Adverse events	X	X	X	X	X	X	X	X	X	X	X	
Vital signs (BP and heart rate), body temperature only if clinically indicated	X	X	X	X	X	X	X	X	X	X	X	Sitting blood pressure and pulse, to be obtained at approximately the same time as ECG measurements or blood sampling. When multiple assessments are scheduled for the same time point, the order of completion should be as follows: ECG, vital signs, and then blood sampling.
ECGs									X			ECGs should be performed before any blood is drawn. Subjects should be supine for approximately 5 to 10 minutes before ECG collection and remain supine but awake during ECG collection.
C-SSRS	X	X	X	X	X	X	X	X	X	X	X	
CCI												

Maintenance Dosing Period (Visits 8-18)												
Visit No.	V8	V9	V10	V11	V12	V13	V14	V15	V16	V17	V18	Comments
Week Relative to Study Drug Start	20	24	28	32	36	40	44	48	52	56	60	All activities should be completed prior to any study dose administration unless otherwise stated below.
Day with Visit Tolerance Interval	140 ± 5	168 ± 5	196 ± 5	224 ± 5	252 ± 5	280 ± 5	308 ± 5	336 ± 5	364 ± 5	392 ± 5	420 ± 5	
Study drug dosed	X	X	X	X	X	X	X	X	X	X	X	Subjects assigned to PRN will be evaluated at every visit to determine if dose needed. Subjects assigned to Q8W will get dosed on odd number visits.
Clinical Efficacy												
PASI	X	X	X	X	X	X	X	X	X	X	X	
sPGA	X	X	X	X	X	X	X	X	X	X	X	
PSSI, if applicable	X	X	X	X	X	X	X	X	X	X	X	Once a subject experiences symptoms related to scalp involvement, this form should be completed at all remaining indicated visits.
Whole body photographs				X					X			If subject has agreed to whole body photographs.
Health Outcomes												
PSS				X					X			
PatGA				X					X			
DLQI				X					X			In addition to the marked visits, DLQI also taken at PRN dosing or rescue treatment visits.
SF-36				X					X			
Laboratory Tests												
Hematology	X	X	X	X	X	X	X	X	X			Unscheduled blood chemistry and hematology panels may be performed at the discretion of the investigator.
Lymphocyte subsets									X			

Maintenance Dosing Period (Visits 8-18)												
Visit No.	V8	V9	V10	V11	V12	V13	V14	V15	V16	V17	V18	Comments
Week Relative to Study Drug Start	20	24	28	32	36	40	44	48	52	56	60	All activities should be completed prior to any study dose administration unless otherwise stated below.
Day with Visit Tolerance Interval	140 ± 5	168 ± 5	196 ± 5	224 ± 5	252 ± 5	280 ± 5	308 ± 5	336 ± 5	364 ± 5	392 ± 5	420 ± 5	
Serum chemistry	X	X	X	X	X	X	X	X	X			Unscheduled blood chemistry and hematology panels may be performed at the discretion of the investigator.
Urinalysis				X					X			
HBV PCR		X			X			X			X	Any enrolled subject who is HBcAb+ will undergo monitoring of HBV PCR. Any subject with a positive HBV PCR test at any time must be discontinued from the study and receive appropriate follow-up medical care, including consideration for antiviral therapy.
Immuno-genicity		X		X		X		X		X		
Serum for LY3074828 concentration (PK)	X	X		X		X		X	X	X		
Urine pregnancy test	X	X	X	X	X	X	X	X	X	X	X	To be performed only on women of child bearing potential.
hsCRP	X	X	X	X	X	X	X	X	X	X	X	
Skin punch biopsy									X			
Serum/ plasma for storage/ exploratory biomarkers	X	X	X	X	X	X	X	X	X	X	X	
CCI		■			■				■		■	

Maintenance Dosing Period (Visits 19-29)												
Visit No.:	V19	V20	V21	V22	V23	V24	V25	V26	V27	V28	V29	Comments
Week Relative to Study Drug Start	64	68	72	76	80	84	88	92	96	100	104	All activities should be completed prior to any study dose administration unless otherwise stated below.
Day with Visit Tolerance Interval	448 ± 5	476 ± 5	504 ± 5	532 ± 5	560 ± 5	588 ± 5	616 ± 5	644 ± 5	672 ± 5	700 ± 5	728 ± 5	
Physical examination & weight				X							X	All physical examinations throughout the study should include a symptom-directed evaluation as well as examination of heart, lungs, and abdomen and visual examination of all skin areas (including genitalia and breast areas).
Concomitant medications	X	X	X	X	X	X	X	X	X	X	X	
Adverse events	X	X	X	X	X	X	X	X	X	X	X	
Vital signs (BP and heart rate), body temperature only if clinically indicated	X	X	X	X	X	X	X	X	X	X	X	Sitting blood pressure and pulse, to be obtained at approximately the same time as ECG measurements or blood sampling. When multiple assessments are scheduled for the same time point, the order of completion should be as follows: ECG, vital signs, and then blood sampling.
ECGs					X						X	ECGs should be performed before any blood is drawn. Subjects should be supine for approximately 5 to 10 minutes before ECG collection and remain supine but awake during ECG collection.
C-SSRS	X	X	X	X	X	X	X	X	X	X	X	
CCI												

Maintenance Dosing Period (Visits 19-29)												
Visit No.:	V19	V20	V21	V22	V23	V24	V25	V26	V27	V28	V29	Comments
Week Relative to Study Drug Start	64	68	72	76	80	84	88	92	96	100	104	All activities should be completed prior to any study dose administration unless otherwise stated below.
Day with Visit Tolerance Interval	448 ± 5	476 ± 5	504 ± 5	532 ± 5	560 ± 5	588 ± 5	616 ± 5	644 ± 5	672 ± 5	700 ± 5	728 ± 5	
Study drug dosed	X	X	X	X	X	X	X	X	X	X	X	Subjects assigned to PRN will be evaluated at every visit to determine if dose needed. Subjects assigned to Q8W will get dosed on odd number visits. For subjects who enter the separate long-term extension study, the Visit 29 dose will be determined by the protocol of that study.
Clinical Efficacy												
PASI	X	X	X	X	X	X	X	X	X	X	X	
sPGA	X	X	X	X	X	X	X	X	X	X	X	
PSSI, if applicable	X	X	X	X	X	X	X	X	X	X	X	Once a subject experiences symptoms related to scalp involvement, this form should be completed at all remaining indicated visits.
Whole body photographs											X	If subject has agreed to whole body photographs.
Health Outcomes												
PSS												X
PatGA												X
DLQI												X
SF-36												X
Laboratory Tests												
Hematology	X				X				X		X	Unscheduled blood chemistry and hematology panels may be performed at the discretion of the investigator.
Lymphocyte subsets											X	

Maintenance Dosing Period (Visits 19-29)												
Visit No.:	V19	V20	V21	V22	V23	V24	V25	V26	V27	V28	V29	Comments
Week Relative to Study Drug Start	64	68	72	76	80	84	88	92	96	100	104	All activities should be completed prior to any study dose administration unless otherwise stated below.
Day with Visit Tolerance Interval	448 ± 5	476 ± 5	504 ± 5	532 ± 5	560 ± 5	588 ± 5	616 ± 5	644 ± 5	672 ± 5	700 ± 5	728 ± 5	
Serum chemistry	X				X				X		X	Unscheduled blood chemistry and hematology panels may be performed at the discretion of the investigator.
Fasting lipid profile											X	Patients should not eat or drink anything except water for 12 hours prior to sample collection. If a patient attends these visits in a nonfasting state, this will not be considered a protocol violation.
Urinalysis	X				X				X		X	
HBV PCR			X			X			X		X	Any enrolled subject who is HBcAb+ will undergo monitoring of HBV PCR. Any subject with a positive HBV PCR test at any time must be discontinued from the study and receive appropriate follow-up medical care, including consideration for antiviral therapy.
Immuno-genicity	X		X		X		X		X		X	
Serum for LY3074828 concentration (PK)	X		X		X		X		X	X	X	
Urine pregnancy test	X	X	X	X	X	X	X	X	X	X	X	To be performed only on women of child bearing potential.
hsCRP	X	X	X	X	X	X	X	X	X	X	X	
Serum/ plasma for storage/ exploratory biomarkers	X	X	X	X	X	X	X	X	X	X	X	

Maintenance Dosing Period (Visits 19-29)												
Visit No.:	V19	V20	V21	V22	V23	V24	V25	V26	V27	V28	V29	Comments
Week Relative to Study Drug Start	64	68	72	76	80	84	88	92	96	100	104	All activities should be completed prior to any study dose administration unless otherwise stated below.
Day with Visit Tolerance Interval	448 ± 5	476 ± 5	504 ± 5	532 ± 5	560 ± 5	588 ± 5	616 ± 5	644 ± 5	672 ± 5	700 ± 5	728 ± 5	
CCI			■			■			■		■	

Follow-up Period (Visits 801-804)					
Visit No.:	V801 a	V802 a	V803 a	V804/ET	Comments
Week Relative to Study Drug Start	108	112	116	120	All activities should be completed prior to any study dose administration unless otherwise stated below.
Day with Visit Tolerance Interval	756 ± 5	784 ± 5	812 ± 5	840 ± 5	
Physical examination & weight				X	All physical examinations throughout the study should include a symptom-directed evaluation as well as examination of heart, lungs, and abdomen and visual examination of all skin areas (including genitalia and breast areas).
Concomitant medications	X	X	X	X	
Adverse events	X	X	X	X	
Vital signs (BP and heart rate), body temperature only if clinically indicated	X	X	X	X	Sitting blood pressure and pulse, to be obtained at approximately the same time as ECG measurements or blood sampling. When multiple assessments are scheduled for the same time point, the order of completion should be as follows: ECG, vital signs, and then blood sampling.
ECGs				X	ECGs should be performed before any blood is drawn. Subjects should be supine for approximately 5 to 10 minutes before ECG collection and remain supine but awake during ECG collection.
C-SSRS	X	X	X	X	
CCI	■	■	■	■	
Clinical Efficacy					
PASI	X	X	X	X	
sPGA	X	X	X	X	
PSSI, if applicable	X	X	X	X	Once a subject experiences symptoms related to scalp involvement, this form should be completed at all remaining indicated visits.
Whole body photographs				X	If subject has agreed to whole body photographs.
Health Outcomes					
PSS				X	
PatGA				X	
DLQI				X	
SF-36				X	
Laboratory Tests					

Follow-up Period (Visits 801-804)					
Visit No.:	V801 a	V802 a	V803 a	V804/ET	Comments
Week Relative to Study Drug Start	108	112	116	120	All activities should be completed prior to any study dose administration unless otherwise stated below.
Day with Visit Tolerance Interval	756 ± 5	784 ± 5	812 ± 5	840 ± 5	
